## **Funder**

This study has been part funded by the Royal Wolverhampton Hospitals NHS Trust Pharmacy Department.

This protocol describes the above study and provides information about procedures for entering participants. Every care was taken in its drafting, but corrections or amendments may be necessary. These will be circulated to investigators in the study. Problems relating to this study should be referred, in the first instance, to the Chief Investigator.

This study will adhere to the principles outlined in the NHS Research Governance Framework for Health and Social Care (2nd edition). It will be conducted in compliance

with the protocol, the Data Protection Act and other regulatory requirements as appropriate.

## **GLOSSARY OF ABBREVIATIONS AND TECHNICAL TERMS**

ACS	Acute coronary syndrome
ADP	Adenosine diphosphate
AE	Adverse event
CABG	Coronary artery bypass graft
ECG	Electrocardiogram
HTPR	High on-treatment platelet reactivity
NSTEMI	Non-ST segment elevation myocardial infarction
PPCI	Primary percutaneous coronary intervention
SAE	Serious adverse event
STEMI	ST-segment elevation myocardial infarction
TIMI	Thrombolysis in myocardial infarction
UA	Unstable angina
VASP	Vasodilator stimulated phosphoprotein phosphorylation

## **KEYWORDS**

Pharmacodynamic  
Pharmacokinetic  
Antiplatelet  
Myocardial infarction  
Clopidogrel  
Prasugrel  
Ticagrelor  
STEMI  
NSTEMI

## 1. LAY SUMMARY

Major heart attacks are caused by a number of factors, the two major of which are furring up of a coronary artery with atheroma and then sudden clot formation on this area leading to a blockage and interruption of blood flow. The clots that lead to heart attacks are largely made of clotting blood cells (platelets) that in health repair blood vessels and inhibit spontaneous bleeding. One of the main treatment strategies for heart attacks is to make these cells less “sticky”. Aspirin is a main stay of treatment at our institution and in addition one of three other antiplatelet agents acting on the same platelet activation pathway (P2Y12 receptor) are used (clopidogrel, prasugrel or ticagrelor). When a patient is admitted with a major heart attack, they are treated with emergency primary percutaneous coronary intervention (PPCI) a technique where a wire and balloon are used to reopen the coronary artery and then usually a stent (a slotted metal tube) is placed to keep the artery open. Aspirin and one of the P2Y12 inhibitor agents are given to prevent further clots and all have been shown to reduce negative events following heart attacks and angioplasty with stent insertion.

All three P2Y12 inhibitor agents are taken in tablet form immediately before the emergency PPCI procedure. It appears that these agents in healthy stable patients take at least 30 min to 2 hours to have an adequate effect. In PPCI patients, often the procedures are performed well within this timescale. Furthermore patients who are having a heart attack may not have normal drug absorption with blood being diverted away from the stomach and gut activity being suppressed by other drugs such as morphine.

In this study patients with major heart attacks will be given one of the three anti-platelet agents (being treated as per normal clinical pathways). Blood samples will be taken to assess the effect of the anti-platelet agents when the balloon opens the artery and after 20 minutes, 60 min and 4 hours after taking the drugs.

A variety of tests will be used to check the activity of the drugs including measuring the concentration of the active component of each of the three anti-platelet agents in the blood.

In total the patients in the study will require up to 4 extra blood tests, each using 15 ml of blood (approximately 3 teaspoons of blood). This will not cause any ill effects but may involve up to 3 extra needle pricks.

One of the major negative occurrences after PPCI is clotting within the stent- this occurs in 0-2% of cases and in other patients is associated with a poor response to these anti-platelet drugs. It is possible that this study will identify which, if any, of the agents used are working during the procedure, given the very short timescales involved. In the future it might be that an intravenous agent will be more valuable in the setting of PPCI.

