Ticagrelor differs from the thienopyridine class of antiplatelet agents (clopidogrel, prasugrel, and ticlopidine) as it does not exist as a prodrug and thus does not require biotransformation by hepatic enzymes before becoming active. Also ticagrelor binds reversibly to P2Y12 receptors leading to a faster onset and offset than clopidogrel (15). The PLATO trial which compared ticagrelor with clopidogrel, demonstrated an improvement in clinical outcome in the ticagrelor group. (16). Moreover, in the RESPOND study, ticagrelor therapy was associated with uniform and superior platelet inhibition in both previously identified clopidogrel responders and nonresponders, and that inhibition, in turn, was associated with an extremely low prevalence of high on-treatment platelet reactivity (17). Ticagrelor has recently received recommendation in the ESC guideline as a front-line treatment option for STEMI and NSTEMI (18,19)

The synthetic hirudin analogue Bivalirudin is a reversible direct thrombin inhibitor with important effects on the coagulation pathways and also inhibits the activity of circulating and clot bound thrombin, thus also having a partial antiplatelet effect. This agent, when used with dual antiplatelet therapy in patients undergoing PPCI for STEMI, appears to confer a survival benefit compared to heparin, IIb/IIIa receptor antagonism and dual antiplatelet therapy (with aspirin and clopidogrel) (20). This benefit is largely due to a reduction in major bleeding. In the Horizon-AMI trial, however, there was a marked increase in early stent thrombosis in the bivalirudin group (from 1.4% vs 0.3 %).

In view of these positive findings many operators now use bivalirudin routinely (as recommended as a possible treatment by NICE guidance TA 230) but to mitigate against the higher risk of stent thrombosis are giving one of the newer P2Y12 antagonists (prasugrel or ticagrelor) which have been shown to lead to lower stent thrombosis rates in other ACS groups (14, 21). Whilst both of these agents have been shown to have a faster onset of action than clopidogrel, there are currently no data on the onset of action required in the setting of PPCI. Ideally a full antiplatelet effect would be evident at the start of the PPCI, whereas in practice dosing of clopidogrel, prasugrel or ticagrelor typically occurs on admission to hospital (possible only 10-20 minutes prior to PPCI).

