### **3. STUDY OBJECTIVES**

- 1) To determine the degree and time-course of platelet inhibition in patients admitted with NSTEMI treated with prasugrel within the first 4 hours of loading. These data will be compared with data already collected on STEMI patients treated with prasugrel to determine whether the condition of STEMI per se reduces the efficacy of prasugrel treatment.
- 2) To demonstrate the degree and time-course of platelet inhibition by ticagrelor given acutely before emergency primary angioplasty for STEMI, during the procedure and in the following 4 hours. This will be compared with a cohort of patients presenting with NSTEMI treated with ticagrelor to determine whether the condition of STEMI per se reduces the efficacy of ticagrelor treatment.

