## 4. STUDY DESIGN

This is a pilot study which is both non-randomised and observational in nature. We plan on recruiting a total of 45 participants into the study who will comprise of patients admitted to New Cross Hospital suffering from an acute coronary syndrome. The study will complete an on-going project (REC ref no. 13/WM/0025 ethical approval granted from South Birmingham Regional Ethics Committee). Whole blood samples will be taken from participants following a single loading dose of an antiplatelet agent once the diagnosis of an ACS has been made. We anticipate the conclusion of subject recruitment in 3 months from the study start date

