### 4.1 STUDY OUTCOME MEASURES

- a) Degree of platelet inhibition measured with VerifyNow™ rapid platelet function analyser
- b) Degree of platelet inhibition measured with VASP flow cytometry
- c) Concentration of prasugrel and ticagrelor active metabolite in plasma measured with liquid chromatography with tandem mass spectrometry.

This study is not powered for clinical outcomes; however clinical data will be recorded.

Clinical endpoints to be recorded for each participant will include:

- d) Angiographic variables –
  - thrombolysis in myocardial infarction (TIMI) flow at end of case,
  - slow flow/no reflow
- e) ECG variables –
  - ST-segment resolution at end of case
- f) Safety endpoints –
  - Death
  - CABG
  - TIMI major and minor bleed (see appendix 1 for bleeding criteria)

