## 7. STATISTICS AND DATA ANALYSIS

All statistical analysis will be performed in collaboration with [name], Professor of biomedical statistics at University of Wolverhampton.

Continuous variables will be compared using parametric and non-parametric tests as appropriate. Dichotomous variables will be compared by Fishers exact test. Logistic regression analysis will be used to predict the significant independent predictors of poor outcome post angiography.

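### Opiate use, which the protocol itself names as a cause of poor drug absorption, is not specified for recording or analysis, so its effect cannot be separated from that of STEMI *per se*

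*Combined protocol and SAP*

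**What the plan says.** Section 3 has two objectives, both directed at STEMI *per se*. The ticagrelor objective compares Group 5 (STEMI) with Group 6 (NSTEMI) "to determine whether the condition of STEMI per se reduces the efficacy of ticagrelor treatment". The prasugrel objective sets new NSTEMI patients (Group 2) against an existing series: "These data will be compared with data already collected on STEMI patients treated with prasugrel". Section 4 describes the design: "This is a pilot study which is both non-randomised and observational in nature". Section 5.2 plans 15 patients per group.

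The lay summary (section 1) offers two reasons for impaired absorption during a heart attack: diversion of blood from the stomach, and "gut activity being suppressed by other drugs such as morphine". Section 2.2 gives only physiological reasons: low blood pressure, reduced splanchnic flow and raised intrinsic platelet activity.

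On data capture, section 4.1 states "This study is not powered for clinical outcomes; however clinical data will be recorded", then lists angiographic, ECG and safety endpoints. Section 6.2 records the time of the loading dose. The schedule in section 6.3.3 lists consent, blood draws and assays. None of these mentions opiates, and sections 5.3 and 5.4 do not restrict them. On analysis, section 7 states "Continuous variables will be compared using parametric and non-parametric tests as appropriate". Its only regression concerns predictors of poor outcome after angiography, and no covariates are named.

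**The concern.** Of the two absorption mechanisms in the lay summary, diverted blood flow belongs to the disease and morphine is a co-treatment. The protocol thus supplies a rival explanation for the difference it hopes to detect. Morphine is also the rival that matters most for these outcomes: by acting on absorption it could alter both the plasma concentrations and the platelet measures, so agreement between the two would not rule it out.

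If opiates are given more often in one group, the group difference contains an opiate component. Slower onset caused by STEMI physiology and slower onset caused by a drug given alongside have different implications, and the study as written offers no way to say which was seen. Timing matters too. With samples at 20 minutes, 60 minutes and 4 hours after loading, a yes/no record without dose and time would be of limited use, and such detail may be hard to recover afterwards.

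**Working it through.** **No plan figure to reproduce.** The documents give no alpha, power, SD or effect size. The only check is 3 groups × 15 = 45, which agrees with section 4. What follows illustrates the consequence for Group 5 v Group 6. The size of the prasugrel STEMI series is not stated.

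**Assumptions (none from the documents).** Opiate use in STEMI, p_S = 60-80%; in NSTEMI, p_N = 10-30%; opiate effect δ = 0.4-1.2 SD of platelet reactivity; two-sided 5% test; STEMI itself has no effect.

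**Step 1: offset in the unadjusted comparison.** Offset = (p_S − p_N) × δ.
- Low: (0.60 − 0.30) × 0.4 = 0.12 SD
- Middle: (0.70 − 0.20) × 0.8 = 0.40 SD
- High: (0.80 − 0.10) × 1.2 = 0.84 SD

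**Step 2: chance of a significant result with no STEMI effect.** Non-central t, 28 df, non-centrality = offset / √(2/15) = offset / 0.365.
- 0.12 / 0.365 = 0.33, rejection 6%
- 0.40 / 0.365 = 1.10, rejection 18%
- 0.84 / 0.365 = 2.30, rejection 60%

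If the SD is taken within opiate strata, mixing treated and untreated patients widens the spread by √(1 + δ²[p_S(1−p_S) + p_N(1−p_N)]/2). For the middle case this is √(1 + 0.64 × 0.185) = 1.058, so the offset is 0.40/1.058 = 0.38 SD and rejection is 17%. For the high case it is √(1 + 1.44 × 0.125) = 1.086, giving 0.84/1.086 = 0.77 SD and 53%.

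**Step 3: price of adjusting.** With equal groups, the squared correlation between STEMI status and opiate use is r² = 0.25(p_S − p_N)² / [p̄(1 − p̄)]. The variance of the STEMI effect is inflated by 1/(1 − r²). In all three cases p̄ = 0.45 and p̄(1 − p̄) = 0.2475.

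| Use, STEMI v NSTEMI | r² | Variance factor | Standard error |
|---|---|---|---|
| 60% v 30% | 0.25 × 0.09 / 0.2475 = 0.091 | 1.10 | +5% |
| 70% v 20% | 0.25 × 0.25 / 0.2475 = 0.253 | 1.34 | +16% |
| 80% v 10% | 0.25 × 0.49 / 0.2475 = 0.495 | 1.98 | +41% |

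With 15 per group, the difference detectable with 80% power is (1.96 + 0.84) × 0.365 = 1.02 SD unadjusted. It becomes 1.02 × 1.05 = 1.07 SD to 1.02 × 1.41 = 1.44 SD adjusted. At 100% v 0% use, r² = 1 and the two effects cannot be separated at all.

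**Step 4: opiate-free patients only.** Expected numbers are 15 × 0.2 = 3 to 15 × 0.4 = 6 STEMI patients, against 15 × 0.7 = 10.5 to 15 × 0.9 = 13.5 NSTEMI patients. Relative to 15 v 15, the standard error is √(1/6 + 1/10.5)/0.365 = 1.40 times as large at 60% v 30%, and √(1/3 + 1/13.5)/0.365 = 1.75 times as large at 80% v 10%.

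**The case against.** **The list in section 4.1 is open.** It covers endpoints, not treatments, and follows a general statement that clinical data will be recorded. Age and weight are absent from it too, although eligibility depends on them. No case record form is supplied, and the appendix flow charts are not shown. This stands. A reader might infer that opiate use will go unrecorded, but the text supports only that recording is not specified. Recording alone would still leave section 7 without an analysis that uses it.

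**Opiates are part of STEMI care, so the unadjusted contrast is legitimate.** This also stands. A reader might infer that without opiate data no STEMI effect can be described at all. In fact the unadjusted comparison does describe the overall difference between the two pathways, co-treatment included. What is lost is the split between its parts, which a narrow reading of *per se* requires. The lay summary sets morphine beside diverted blood flow, so the aim is itself ambiguous and should be stated.

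**Bivalirudin looks like a second instance.** Section 2.1 says "many operators now use bivalirudin routinely" and describes the drug as "thus also having a partial antiplatelet effect". The documents do not support giving it equal weight. Nowhere do they say that study patients receive it. Section 2.2 describes both P2Y12 tests as specific to that receptor, and nothing suggests an effect on plasma concentrations. Any antiplatelet action would tend to hide a STEMI deficit, not imitate one. The IIb/IIIa antagonists in section 2.1 deserve a similar note, since VerifyNow reads aggregation (section 6.3.1).

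**It is a small pilot.** That limits how much adjustment can achieve, but small size does not remove bias.

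**Conclusion.** The point holds as a cheap improvement. In a non-randomised comparison aimed at STEMI *per se*, the protocol names a co-treatment that impairs absorption, and the available text neither specifies its recording nor plans an analysis that accounts for it. Followed as written, the plan can support a statement about the STEMI pathway but not about STEMI *per se*.

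The size of any bias is illustrative only. The offset of 0.12-0.84 SD, with rejection in 6-60% of studies (at most about 53% if the SD is within strata), rests wholly on assumed use rates and effect. A reader might infer that an observed difference will be an opiate artefact, or will be misreported as a disease effect. The documents do not show this: they do not say how many patients in either group receive opiates, and NSTEMI patients may receive them too. The supportable statement is that the two cannot be separated.

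For prasugrel, the STEMI data already exist, and the documents do not show whether opiate use was captured.

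**What to change.** - **Sections 4.1 and 6.2:** for Groups 2, 5 and 6, record any opiate given, its dose, and its time relative to the loading dose. Record peri-procedural bivalirudin and IIb/IIIa inhibitor use as a minor descriptive item.
- **Existing prasugrel STEMI data:** check whether opiate use, dose and time can be retrieved, and state the result.
- **Section 7:** report opiate use by group. Keep the unadjusted STEMI v NSTEMI comparison, labelled as the STEMI-pathway contrast. Pre-specify one opiate-adjusted sensitivity analysis. Show opiate-free patients descriptively only, since about 3-6 v 10-14 patients cannot carry a test.
- **Section 3 and reporting:** avoid *per se* wording where opiate use barely overlaps between groups or was not captured. This includes the prasugrel comparison if the data cannot be retrieved.

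**Cost:** two or three extra data items per patient, a retrieval check on the earlier series, and one more analysis. No treatment changes. The price of adjustment is more than one degree of freedom: under the assumed use rates the adjusted standard error is about 5-41% larger, so that estimate will be imprecise and should be presented as such.

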## 2. INTRODUCTION

### 2.1 BACKGROUND

The success of modern treatment for ST-segment elevation myocardial infarction (STEMI) is dependent, in part, on the adequate suppression of platelet activity. Primary percutaneous coronary intervention (PPCI) for STEMI management has led to marked reductions in morbidity and mortality (1). Aspirin is the mainstay anti-platelet agent (2) which acts by irreversible acetylation and inhibition of the COX-1 enzyme, thereby reducing the production of thromboxane A2, a potent platelet activator. The advent of the platelet P2Y12 inhibitors led to further improvement in outcomes in patients with acute coronary syndromes (ACS) undergoing PCI with reduced ischaemic complications (3) albeit at an increase in rate of bleeding complications. Both of these agents have a synergistic effect on platelet function with the addition of clopidogrel to aspirin leading to approximately 20% reduction in negative cardiovascular events (4). Activation of platelets leads to a conformational change in the surface glycoprotein IIb/IIIa receptor that allows cross bridging with fibrinogen and rapid aggregation (platelet thrombus formation).

During PPCI thrombus formation and dispersion can have a major impact on outcome. Intravenous platelet IIb/IIIa receptor antagonists such as abciximab were initially shown to have a positive impact on primary angioplasty outcomes leading to a class IIa indication within the European Society of Cardiology (ESC) guidelines for use in the treatment of STEMI with angioplasty (5).

As oral antiplatelet inhibition has improved (specifically with the addition of clopidogrel, prasugrel or ticagrelor) there has been a concomitant reduction in the use of intravenous IIb/IIIa agents during PCI for patients with ACS. This has been partly informed by later studies suggesting that the additive value of these agents to dual anti-platelet therapy is questionable (6). In addition, the extra bleeding complications are seen by some to be excessive (7).

Clopidogrel, the most commonly used P2Y12 inhibitor has been shown to reduce ischaemic complications in patients with ACS both with and without PCI (8), but there are significant issues regarding both the uniformity of action across patients (9) and also the speed of onset of action of this agent (10). There are a variety of causes for the variable response to clopidogrel amongst subjects, leading to high on-treatment platelet reactivity (HTPR), but key is the two stage hepatic conversion to its active metabolite with variances in the CYP 450 isoenzymes (particularly 2C19) playing a major role. As many as 40 % of treated patients may have a suboptimal response to clopidogrel and these patients are more likely to suffer recurrent ischaemic events and in particular stent thrombosis (11). Notably one of the first papers demonstrating this problem involved PPCI patients (12). Further large scale trials have identified the risk of poor clopidogrel activity with negative outcomes in PPCI patients (13).

Prasugrel, a newer thienopyridine has a greater uniformity of action and a more rapid onset of action than clopidogrel. This appears to lead to improved outcomes in patients

treated with PCI for ACS and in particular a reduction in stent thrombosis (TRITON-TIMI 38).(14). NICE guidelines (TA 182) now recommend the use of prasugrel in treatment of patients either over the age of 75 or over 60kg undergoing PPCI. The TIMI-TRITON 38 trial was however biased toward prasugrel in that the majority of drug dosing was performed at the end of the PCI procedure, and therefore there would have been less P2Y12 activity for a number of hours after the administration of the agent with the slower onset of action. Also the majority of patients included were Non-STEMI (NSTEMI) or convalescent STEMI patients undergoing PCI. In the STEMI subgroup (again with a 2:1 convalescent to acute ratio) there was no advantage of the newer agent seen, possibly due to issues with drug absorption and metabolism (14).

Ticagrelor differs from the thienopyridine class of antiplatelet agents (clopidogrel, prasugrel, and ticlopidine) as it does not exist as a prodrug and thus does not require biotransformation by hepatic enzymes before becoming active. Also ticagrelor binds reversibly to P2Y12 receptors leading to a faster onset and offset than clopidogrel (15). The PLATO trial which compared ticagrelor with clopidogrel, demonstrated an improvement in clinical outcome in the ticagrelor group. (16). Moreover, in the RESPOND study, ticagrelor therapy was associated with uniform and superior platelet inhibition in both previously identified clopidogrel responders and nonresponders, and that inhibition, in turn, was associated with an extremely low prevalence of high on-treatment platelet reactivity (17). Ticagrelor has recently received recommendation in the ESC guideline as a front-line treatment option for STEMI and NSTEMI (18,19)

The synthetic hirudin analogue Bivalirudin is a reversible direct thrombin inhibitor with important effects on the coagulation pathways and also inhibits the activity of circulating and clot bound thrombin, thus also having a partial antiplatelet effect. This agent, when used with dual antiplatelet therapy in patients undergoing PPCI for STEMI, appears to confer a survival benefit compared to heparin, IIb/IIIa receptor antagonism and dual antiplatelet therapy (with aspirin and clopidogrel) (20). This benefit is largely due to a reduction in major bleeding. In the Horizon-AMI trial, however, there was a marked increase in early stent thrombosis in the bivalirudin group (from 1.4% vs 0.3 %).

In view of these positive findings many operators now use bivalirudin routinely (as recommended as a possible treatment by NICE guidance TA 230) but to mitigate against the higher risk of stent thrombosis are giving one of the newer P2Y12 antagonists (prasugrel or ticagrelor) which have been shown to lead to lower stent thrombosis rates in other ACS groups (14, 21). Whilst both of these agents have been shown to have a faster onset of action than clopidogrel, there are currently no data on the onset of action required in the setting of PPCI. Ideally a full antiplatelet effect would be evident at the start of the PPCI, whereas in practice dosing of clopidogrel, prasugrel or ticagrelor typically occurs on admission to hospital (possible only 10-20 minutes prior to PPCI).

During PPCI (particularly using bivalirudin rather than i.v. IIb/IIIa antagonists) it is likely therefore that patient's would be advantaged by rapid P2Y12 antagonism. Currently there are no data concerning the comparative rapidity of clinical effect of these agents in the setting of an acute STEMI when compared to other groups.

